9.5 Study Conduct

The study visits are to be conducted as shown in the Schedule of Events, Appendix [15.1](#).

Study completion or the reason for study discontinuation will be recorded in the source document and the eCRF.

9.5.1 Unscheduled Visits

Unscheduled visits and tests are permitted as needed to assess AEs/SAEs throughout the study. Unscheduled visits and tests are also permitted as needed to assess AEs/ SAEs with onset within two (2) weeks after the final study visit providing the AE is considered related to study drug

9.6 Compliance with Study Procedures

The time at which study procedures are conducted should follow the protocol timelines as closely as possible. However, it is recognized in a clinical setting that protocol-specified timings may not occur exactly as specified in the protocol, particularly when conducted remotely by the subject. Provided that activities are carried out within the identified windows it will not be necessary to file a protocol deviation. Remote visits such as a telemedicine visit may be conducted to collect as much information as possible remotely. A home visit or return to the clinical site or an out-patient laboratory may be arranged for safety labs or other assessments, when required. Telemedicine or other remote technique is to be utilized to ensure subject compliance when subject is performing self-collection of study assessments.

9.7 Early Withdrawal from the Study

A subject may withdraw from the study at any time for any reason or for one of the reasons listed below. The Sponsor or Investigator may also terminate a subject's study participation after discussion with the other party if it is believed it would be unsafe for the subject to continue in the study.

Subjects must discontinue study medication if any of the following events occur:

- Significant protocol violation or non-compliance, either on the part of the subject or the investigator or other site personnel;
- Decision of the Investigator or Sponsor that removal is in the subject's best interest;
- Severe unrelated medical illness or complication;
- Safety reasons/ significant adverse event;
- Subject request (withdrawal of consent);
- Sponsor decision.

Collect/conduct all scheduled evaluations even for subjects who discontinue study medication prior to completing the treatment period unless consent is withdrawn.

9.8 Early Termination of the Study

If the Sponsor or an Investigator believes it would be unsafe to continue the study, or for any reason at the Sponsor's request, the study may be terminated at that site or the entire study terminated after discussion with the other parties.

The Sponsor will provide a written statement to the IRB and the relevant regulatory authority with the reasons for termination of the study. This will be conducted within 15 days of the decision to terminate the study.

If the study is terminated, a close out monitoring visit will be performed and applicable procedures will be carried out to close the trial site(s).

9.9 Non-Childbearing Potential

Women of non-childbearing potential are defined as those who have no uterus, ligation of the fallopian tubes, or permanent cessation of ovarian function due to ovarian failure or surgical removal of the ovaries. Documentation of surgical procedure or physical examination is required for subjects who have had a hysterectomy or tubal ligation. A woman is also presumed to be infertile due to natural causes if she has been amenorrheic for greater than 12 months and has an FSH greater than 40 IU/L. In the absence of such documentation, a negative serum pregnancy test is required for inclusion into the study.

10 ADVERSE EVENT REPORTING

An adverse event is any untoward medical occurrence in a patient or clinical trial subject administered a medicinal product and which does not necessarily have a causal relationship with this treatment. An AE can therefore be any unfavorable and unintended sign (including an abnormal laboratory finding), symptom, or disease temporally associated with the use of the medicinal product, whether or not considered related to the medicinal product.

Events that occur prior to first dose will be entered as medical history; events that occur after first dose will be entered as adverse events (AEs) on the AE form.

Subjects will be questioned and observed for evidence of AEs, whether or not judged by the Investigator or designated person to be related to study drug. All AEs will be documented in the subject's medical record and CRF. For any pre-existing condition or abnormal laboratory finding that changes in severity after dosing, this change should be recorded as an AE. New abnormal laboratory findings that are clinically significant are considered AEs. Investigators and site staff are to elicit from the subject and note any signs or symptoms of mucositis and thrombocytopenia (see Section 10.8).

Adverse events will be collected from the time of first dose through Day 29. After Day 29, collect/record only Serious Adverse Events (SAEs) which are assessed by the Investigator or designated person to be related to study drug and have an onset within 14 days of study completion (Day 29 or earlier if discontinue prior to Day 29). AE details are to be documented including start and stop date and times, whether continuous or intermittent, severity, any intervention utilized to correct the event (e.g., medication, surgery, or other therapy), outcome and the relationship to the study drug.

AEs identified in the protocol as critical to the evaluation of safety must be reported to the Sponsor by the Investigator according to the reporting requirements within the time periods specified in the protocol.

AEs determined by the Investigator to be related to study drug must be followed until resolution or until they are considered stable or for at least 30 days after discontinuation of study drug.

Abnormal laboratory values or test results occurring after study enrollment constitute AEs only if they induce clinical signs or symptoms, are considered clinically significant, are Grades 3 or 4, or require therapy.

If a death occurs during the SAE reporting period, the cause of death such as pneumonia, ARDS, or respiratory failure, is considered as the AE and the death is considered its outcome. Death should be considered an outcome, not an event. The event or condition leading to death should be recorded and reported as a single medical concept on the AE eCRF. Generally, only one such event should be reported. "Fatal" will be recorded as the outcome of this respective event; death due to an outcome of an AE will not be recorded as separate event. If the primary cause of death is disease progression, the cause of death should be clearly identified as COVID-19.

In cases of surgical or diagnostic procedures, the condition leading to the procedure is considered as the AE instead of the procedure itself. Each AE will be coded by the Sponsor from the verbatim text to a preferred term using a thesaurus based on the Medical Dictionary for Regulatory Activities (MedDRA). For example, record appendicitis, not appendectomy.

The following guidelines will be followed for the recording and reporting of adverse and serious adverse events.

1. The medical history section of the case report form will serve as the source document for baseline events.
 - a. Baseline events are any medical condition, symptom, or clinically significant lab abnormality present before the informed consent is signed.
 - i. If exact start date is unknown, month and year or year may be used as the start date of the baseline event.
2. Adverse events occurring after first dose are to be recorded in the eCRF using the AE form.
3. Serious adverse events will be reported to the local IRB according to institutional policy.

The *NIH Division of AIDS (DAIDS) Table for Grading the Severity of Adult and Pediatric Adverse Events, Corrected Version 2.1 (July 2017)* (<https://rsc.niaid.nih.gov/sites/default/files/daidsgradingcorrectedv21.pdf>) will be used for adverse event reporting.

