	
Investigator or designated person to be related to study drug. Treatment-emergent adverse events will be those with an onset after the date and time of first treatment.
 
Subjects who develop Grade 3 or 4 toxicities or SAEs are to be re-evaluated every 2 days, as feasible, until the toxicity returns to Grade ≤ 2 severity.
 
During assessment for adverse events, investigators and site staff are to elicit from the subject any signs or symptoms of mucositis or thrombocytopenia, e.g.:
 
• Ecchymosis/purpura/petechiae• Epistaxis• Hemoptysis• Hematuria• Gingival bleeding• Prolonged bleeding time from needle sticks, abrasions or lacerations• Hematemesis• Rectal bleeding• Blood in stool• Any other unusual bleeding noted by the subject or caregiver
Stopping Criteria	
Individual Criteria:
 
• Participants who develop a Grade 3 toxicity that is assessed by the investigator to be related to the study drug are to be permanently discontinued from study treatment.• Participants who develop a Grade 4 toxicity, regardless of relatedness to study drug, are to be permanently discontinued from study treatment. 
Study-Level Stopping Criteria:
 
Study enrollment is to be paused if any of the below criteria are met:
 
• If ≥ 3 subjects develop the same related Grade 4 (life-threatening) adverse event or laboratory abnormality;• If ≥ 5 subjects develop the same related Grade 3 or 4 adverse event or laboratory abnormality;• If ≥ 10 subjects develop any related Grade 3 or 4 adverse event or laboratory abnormality. 
All adverse events will be reviewed by the DMC during their reviews. Following assessment by the Data Monitoring Committee (DMC), the DMC will determine whether to stop the study, amend the protocol, or continue the study per protocol.

Statistical Analysis	
A separate, detailed statistical analysis plan (SAP) will be finalized prior to locking the database. All analyses of safety and efficacy for this study will be descriptive in nature and presented by group. Subject demographics and baseline characteristics will be summarized. Subject data listings will also be provided.
 
Summaries for quantitative variables will include the mean, median, quartiles,

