3.6 Risks Associated with Participation in the Clinical Study

In studies utilizing the weekly schedule of administration of high-dose brequinar in patients with refractory solid tumors, reversible myelosuppression, in particular thrombocytopenia, and mucositis have been the primary dose-limiting toxicities. In addition, skin rash, nausea/vomiting, fatigue, and leukopenia have been dose-limiting in trials utilizing other schedules of brequinar administration. However, these effects were self-limiting, transient, required treatment in few cases, and resolved following discontinuation of dosing. These adverse effects have been associated with higher doses of brequinar given via the intravenous route and for longer durations than the 100 mg dose and 5-day regimen proposed for this study.

In addition to studying a higher risk population with symptomatic COVID-19, a comprehensive safety monitoring plan will be utilized in this study to assess the ongoing safety and well-being of participants (see Section 10.8).

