3.7.1 CYP Interactions

No formal clinical drug-drug interaction studies have been performed for brequinar with medications commonly used in treating hematologic malignancies. The nonclinical studies performed to date have demonstrated there is no first-pass metabolism and there have been no apparent hepatotoxic effects in the clinical studies. Brequinar itself does not appear to be a substrate for metabolism by cytochrome P450 enzymes when tested under a variety of conditions. (See Brequinar IB [\[5\]](#); nonclinical data on file with Clear Creek).

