8.2.1 Safety/Tolerability

Safety/tolerability is assessed for each subject at each study visit. The *NIH Division of AIDS (DAIDS) Table for Grading the Severity of Adult and Pediatric Adverse Events, Corrected Version 2.1 (July 2017)* will be utilized for AE reporting. All appropriate treatment areas should have access to a copy of the criteria.

Adverse events (AEs) commonly observed in patients treated with brequinar are provided in the Investigator's Brochure (IB) and include thrombocytopenia, nausea, anemia, diarrhea, vomiting, leukopenia, stomatitis, rash, granulocytopenia, fatigue, and infection. In a study of 209 cancer subjects treated once-weekly (DuP 785-012, see Brequinar IB [5]), the deaths of three patients were attributed to study drug toxicity (two to hemorrhage, one following acute renal failure). Severe toxicities grades (Grades 3 to 4) which typically led to discontinuation in this study included hematologic toxicities (anemia, thrombocytopenia, leukopenia, granulocytopenia), digestive system toxicity (nausea, vomiting, stomatitis, others including gastric hemorrhage) and mucositis.

In three oncology studies with five consecutive days of intravenous (IV) brequinar dosing in 168 subjects (Study 785-001 [14], 785-003 [15], and 785-005 [16]) there were no toxic deaths. For subjects from these three studies who were treated with a daily dose of 100 mg or below (as will be dosed in CCB-CRISIS-02), AEs through 21 days showed that 2 of 39 subjects (5.1%) had a severe (Grades 3 or 4) AE related to study drug (1 subject each with hyperbilirubinemia and hyperglycemia), and no subjects discontinued from the study due to a study drug-related AE. The few study drug related AEs through 21 days at or below the 100 mg dose from these three studies included 2 subjects each with nausea, vomiting, and creatinine elevated and one subject each with thrombocytopenia and diarrhea. When only studies with oral dosing were considered at this dose level (Studies 785-022 [17], 785-031 [18], and 785-034 [19]), the study drug related AEs through 21 days (each observed in one subject only) included diarrhea, headache, nausea, pruritus, abdominal pain, anorexia, chest pain, dry mouth, fatigue, keratosis, stomatitis, and vomiting. See brequinar IB [5].

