10.8 Safety Monitoring for Hematologic Toxicities

Myelosuppression is a known effect of DHODH inhibition that is associated with prolonged exposure and high doses. To reduce the risk of this effect with brequinar in COVID-19 subjects, the extensive brequinar safety database with over 1,000 patients has been evaluated to select a dose level expected to be safe and well tolerated with regard to hematologic toxicity. In addition to enhancing safety by

selecting a relatively brief 5-day exposure and a low brequinar dose, all subjects in the clinical trial will be under the care of highly qualified medical personnel. Clinically significant out-of-range laboratory results will be reported as adverse events.

In addition to real time assessments by the treating clinical team, the Covance Medical Monitor will assess the available hematology data on a periodic basis to identify any pathologic trends or safety issues. Any apparent increase in the expected rate or severity of hematologic safety events will be discussed with the Principal Investigators and the Sponsor. In addition, the Data Monitoring Committee (DMC) will assess available hematology data on a periodic basis to independently assess any pathologic trends or safety issues. If the rate or severity of hematologic toxicities appears to be above the expected rate or the severity appears worse than that expected, the trial enrollment will be suspended and no further subjects will be treated while a comprehensive data review is conducted. Depending on the outcome of the safety review the study may be stopped, the design adjusted, or the study may continue as designed. Individual and Study stopping rules are provided in [Section 8.4](#).

Safety laboratory results are to be initially assessed in real time by the Principal Investigator or designated person. Any study drug-related clinically significant out-of-range laboratories or study drug-related adverse events will be followed as needed until resolution or stable.

The in-clinic assessments and telemedicine/phone call visits will specifically ask about possible hematologic toxicity including any evidence of the list below. Subjects will be provided with a list of the following events in lay terms and will be instructed to call the research team if any of these events occur.

- Ecchymosis/purpura/petechiae
- Epistaxis
- Hemoptysis
- Hematuria
- Gingival bleeding
- Prolonged bleeding time from needle sticks, abrasions or lacerations
- Hematemesis

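### Staff are sent to Section 10.8 to elicit mucositis, but its prompt and call-in list holds only bleeding signs; the Medical Monitor's periodic review there also leaves out chemistry

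*Protocol*

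**What the plan says.** All references are to Protocol v5.0.

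- **Section 3.6** says of the weekly high-dose oncology schedule that "reversible myelosuppression, in particular thrombocytopenia, and mucositis have been the primary dose-limiting toxicities". It then refers the reader to Section 10.8 for the trial's safety monitoring.
- **Section 10** tells staff: "Investigators and site staff are to elicit from the subject and note any signs or symptoms of mucositis and thrombocytopenia (see Section 10.8".
- **Synopsis, Safety/Tolerability** tells staff to "elicit from the subject any signs or symptoms of mucositis or thrombocytopenia, e.g", followed by a list of signs.
- **Section 10.8** is titled for hematologic toxicities. It says: "The in-clinic assessments and telemedicine/phone call visits will specifically ask about possible hematologic toxicity including any evidence of the list below". The list is also given to subjects in lay terms, with an instruction to call the research team if any item occurs.
- **Sections 5 and 9.4** schedule calls on Days 2, 3, 5, 6 and 7 that name both thrombocytopenia and mucositis. Section 5 attaches its pointer to 10.8 to thrombocytopenia alone.
- **Section 10.8** also says that "the Covance Medical Monitor will assess the available hematology data on a periodic basis to identify any pathologic trends or safety issues". The DMC trend review and the enrollment-suspension sentence in that section are likewise worded for hematology.
- **Section 8.2.1** reports that, at 100 mg/day or below in three 5-day intravenous studies, "2 of 39 subjects (5.1%) had a severe (Grades 3 or 4) AE related to study drug (1 subject each with hyperbilirubinemia and hyperglycemia".

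**The concern.** The plan names two toxicities to be sought and gives concrete signs for only one. For staff this is a missing aid, because they are still told to ask about mucositis. For subjects it is a missing instruction: someone with mouth sores who follows the list as given has no listed reason to call.

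The design relies on reporting. Many contacts are by telephone or telemedicine, and the only scheduled physical-examination check is at Screening and is self-reported. SAP Section 7.7.2 tabulates adverse events as reported, so what is prompted shapes what the tolerability tables can show.

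The second matter is narrower. A periodic look for trends is most useful where earlier signals exist. At this dose level the severe related events that the protocol itself cites were chemistry findings, which the Medical Monitor's periodic review does not name.

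**Working it through.** **1. Count the prompts.** The list in 10.8 reads, item by item:

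1. ecchymosis/purpura/petechiae
2. epistaxis
3. hemoptysis
4. hematuria
5. gingival bleeding
6. prolonged bleeding
7. hematemesis
8. rectal bleeding
9. blood in stool
10. other unusual bleeding

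All 10 are bleeding or bruising signs and 0 of 10 is a mucositis sign. Gingival bleeding and hematemesis can accompany mucosal injury, but they are still bleeding signs, and the catch-all item is limited to bleeding. The synopsis list has the same ten items. The word mucositis does not occur in Section 10.8, and no other section lists a mucositis sign.

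**2. Where the pointer leads.**

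| Place | What it links to the bleeding list |
|---|---|
| Synopsis | mucositis or thrombocytopenia |
| Section 10 | mucositis and thrombocytopenia |
| Section 5 | thrombocytopenia only |
| Section 9.4 | bleeding examples for thrombocytopenia; mucositis named separately, no examples |
| Section 10.8 | hematologic toxicity only |

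These five places do not agree. On any reading of the pointer, mucositis has a name but no signs.

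**3. When the call-in list carries the load.** The Schedule of Events has adverse-event contact on each of Days 1 to 8, then Days 12, 15, 22 and 29. The gaps after Day 8 are 12 - 8 = 4, 15 - 12 = 3, 22 - 15 = 7 and 29 - 22 = 7 days. Between those contacts, detection depends on the subject calling.

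**4. Reproduce the cited rates (8.2.1, 3.5.2).**

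- Related Grade 3-4 events: 2/39 = 5.13%, stated as 5.1%. Exact (Clopper-Pearson) 95% CI 0.6% to 17.3%.
- Thrombocytopenia, mild: 1/39 = 2.56%, stated as 2.6%.
- Related Grade 3-4 events that were chemistry: 2 of 2. Hematologic: 0/39, exact 95% CI 0% to 9.0%.
- At 2/39, the expected number among about 50 brequinar subjects is 50 x 2/39 = 2.6, and P(at least one) = 1 - (37/39)^50 = 93%.

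**5. How far the fixed pause counts in 8.4.2 reach.** These counts do include chemistry. With X ~ Binomial(50, p), P(X >= k) is the sum over j = k to 50 of C(50, j) p^j (1 - p)^(50 - j). The calculation assumes 50 brequinar subjects and no related events attributed in the placebo arm.

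| Criterion | Cited rate | Assumed higher rates |
|---|---|---|
| >= 10 with any related Grade 3-4 | 0.02% at 5.1% | 2.5% at 10%; 56% at 20% |
| >= 5 with the same related Grade 3-4 | 0.9% at 2.6% | 10% at 5%; 57% at 10% |

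The 5%, 10% and 20% rates are assumptions used to show a range. A rough doubling of the cited rates would usually not reach either count. The third criterion, three subjects with the same related Grade 4 event, could act sooner, but the documents do not split the two cited events by grade.

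**The case against.** Three objections have force.

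**Mucositis is already asked about.** Section 10 and the synopsis require it to be elicited by name, Sections 5 and 9.4 name it for five calls, and the synopsis list is offered only as examples. This stands. A reader might infer that sites never ask about mucositis, or that the trial is biased towards finding none. The documents support neither: the instruction to ask is explicit, and no figure shows how many cases a missing sign list would lose. What survives is the absence of signs and the subject's call-in list, which the named instruction to staff does not repair.

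**Chemistry is well covered elsewhere.** A reader might infer that chemistry goes unwatched. It does not. Results are reviewed within 48 hours of receipt (9.4) and assessed in real time, with related out-of-range values followed (10.8). Individual discontinuation and re-evaluation apply to any toxicity (8.4.1), and the pause counts take any related Grade 3-4 abnormality (8.4.2). The DMC reviews all adverse events and safety laboratories (10.9, 10.9.1), with two reviews as a minimum (synopsis). Only the periodic trend reviews and the suspension sentence in 10.8 are worded for hematology. A bleeding emphasis is also understandable: 8.2.1 attributes two hemorrhage deaths to drug toxicity in the 209-subject weekly study.

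**The earlier data are thin.** The contrast between chemistry and hematology rests on two events in oncology patients dosed intravenously, whereas this trial doses orally. This stands.

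Two apparent contradictions should not be pressed. Section 3.5.2 reports no mucositis in the 39 subjects, while 8.2.1 mentions one stomatitis in oral studies; it gives neither grade nor schedule for those studies, so both can be true. Section 3.7.1 states that "there have been no apparent hepatotoxic effects in the clinical studies"; one related hyperbilirubinemia does not by itself show hepatotoxicity.

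**Conclusion.** The point holds as a gap in the detection aids. Mucositis is to be elicited, yet 0 of the 10 listed signs concerns it, and subjects are not told to call about oral or mucosal signs. The consequence is greatest after Day 8, with gaps of 3 to 7 days between scheduled contacts. The size of any under-detection cannot be estimated from the documents. Mucositis was a primary dose-limiting toxicity on a high-dose weekly schedule, and Section 3.6 associates these effects with higher intravenous doses and longer durations, so the absolute risk here may be low.

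The chemistry point is secondary. The Medical Monitor's periodic review omits the data type in which both cited related Grade 3-4 events fell (5.1%, interval 0.6% to 17.3%). Other safeguards cover chemistry, but two of the three fixed counts would usually not be reached by a doubling of the cited rates. This rests on two events and on the assumed rates shown.

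**What to change.** - In Section 10.8 and the synopsis, add mucositis signs to the elicitation list, for example mouth or throat sores, oral pain and pain on swallowing. Put the same items, in lay terms, on the subject's call-in list.
- In 10.8, widen the instruction to "specifically ask about possible hematologic toxicity including any evidence of the list below" so that it covers mucositis as well as hematologic toxicity.
- Align the pointers in the synopsis and Sections 5, 9.4 and 10 so that each leads to a place where mucositis signs are listed.
- Extend the Medical Monitor's periodic review in 10.8 to the chemistry data.
- The sponsor should reconcile the scope of the 10.8 suspension sentence with 8.2.1 and 8.4.2. No new stopping rule is proposed here.

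The cost is protocol wording and a reprinted subject list. Chemistry is already drawn with hematology and sent to the same central laboratory, so no new sampling is needed. The downside is a few more calls, some prompted by COVID-19 sore throat, which the symptom assessment already records.
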